3.0	
 Updated section 7.8 to mention the primary and secondary endpoint analysis Updated section 7.9.3 to allow for analysis of some additional objectives in the PAS at 3-months Updated sections 7.9.3.5, 7.9.3.6, 7.9.3.7, 7.9.3.9, 7.9.3.10, 7.9.3.13, 7.9.3.14, 7.9.3.15, 7.9.3.16, 7.9.3.17, 7.9.3.18, 7.9.3.19, 7.9.3.20, 7.9.3.21, 7.9.3.22 to include potential analysis of objective in the PAS at 3-months. 	[REDACTED]
4.0	
 Version date on title page corrected from 13-JAN-2023 to 27-JUL-2023 	[REDACTED]

2. List of Abbreviations and Definitions of Terms

Abbreviations should be indicated in parentheses at first appearance in the text. Abbreviations should appear in alphabetical order.

Abbreviation	Definition
ACS	All Consented Set
AE	Adverse Event
CCS	Complete Case Set
CIP	Clinical Investigation Plan
CL	Closed Loop
ECAP	Evoked Compound Action Potential
[REDACTED]	[REDACTED]
FAS	Full Analysis Set
INS	Implanted Neurostimulator
ITT	Intention-to-treat
MCS	Mental Component Summary
MedDRA	Medical Dictionary and Regulatory Affairs
MI	Multiple Imputation
[REDACTED]	[REDACTED]
[REDACTED]	[REDACTED]
OL	Open Loop

Abbreviation	Definition
PAS	Primary Analysis Set
PCS	Physical Component Summary
[REDACTED]	[REDACTED]
[REDACTED]	[REDACTED]
[REDACTED]	[REDACTED]
[REDACTED]	[REDACTED]
SAP	Statistical Analysis Plan
SCS	Spinal Cord Stimulation
[REDACTED]	[REDACTED]
[REDACTED]	[REDACTED]
[REDACTED]	[REDACTED]
VAS	Visual Analogue Scale

3. Introduction

Spinal Cord Stimulation (SCS) is a therapy for the treatment of chronic pain that relies on the application of mild electrical stimulation delivered to the dorsal column fibers of the spinal cord via a lead or leads implanted in the epidural space. Several technologies have been developed for SCS, one of which is the closed-loop algorithm. The closed-loop algorithm uses the evoked compound action potential (ECAP), which is the spinal cord’s physiological response to stimulation, to adjust the amplitude to stimulation, if required.

The purpose of the Closed Loop SCS Study is to further our understanding of closed-loop SCS in patients implanted with the Inceptiv INS. The Closed-Loop SCS study is a prospective, multi-center, randomized, single-blind, investigational, feasibility study. This is a first-in-man study since the fully implantable Inceptiv device has not been studied in humans.

This Statistical Analysis Plan (SAP) is based on the Evaluation of Evaluation of Long-Term Patient Experience with a Medtronic Closed-Loop SCS System (Closed-Loop SCS study) Clinical Investigation Plan (CIP). The SAP presents the details of the methods to be used to analyze and report the study results of the Closed-Loop SCS study, protocol number MDT21017.

4. Study Objectives

4.1 Primary Objective

To demonstrate that the proportion of low-back and leg pain subjects having a reduction in overstimulation sensation with Neuro Sense On compared to Neuro Sense Off, at the randomization and in-clinic testing visit, exceeds a performance goal of 50%.

4.2 Secondary Objectives

1. To characterize the efficacy of spinal cord stimulation (SCS) therapy for the treatment of overall pain (for low-back and/or leg pain subjects) by evaluating the efficacy responder rate. The

efficacy responder rate is defined as the percentage of implanted subjects who experience at least a 50% improvement in overall pain, as measured by the Visual Analogue Scale (VAS), from Baseline to the 3-Month Visit.

2. To characterize the efficacy responder rate within in each type of pain (low-back or leg) for low-back and/or leg pain subjects, as measured by the pain-specific VAS, from Baseline to the 3-Month Visit.

[Redacted text block containing multiple paragraphs of blacked-out content]

5. Investigation Plan

The study is expected to be conducted at up to ten study sites located in Australia. Up to 90 subjects will be enrolled in the study to ensure up to 50 subjects with low-back and/or leg pain and up to 10 subjects with upper limb and neck pain are implanted with the study device. Up to 100 Inceptiv devices may be used in the study. Based on previous studies of this scope and magnitude, it is estimated that each study site will enroll approximately 9 subjects. To reduce the possibility of atypical results from a site overly influencing the study, no more than 20% of the total implanted population will be from each site unless the site gets pre-approval from Medtronic for additional enrollments.

Subjects will be enrolled, and baseline data will be collected. Those meeting all inclusion criteria and no exclusion criteria will undergo a device trial. Subjects with sufficient pain relief during the trial will be implanted with the study device and undergo Device Optimization for 1-Month. Approximately 1-Month post Device Activation, subjects will undergo in-clinic testing. Subjects will be randomized at the in-clinic visit to one of the two sequences: Neuro Sense On followed by Neuro Sense Off or Neuro Sense Off followed by Neuro Sense On. Subjects will be blinded to the settings tested. In each setting, subjects will perform a series of activities and asked to rate the intensity of the overstimulation sensation they experienced while performing the activity using a 5-point Likert scale.

It is recommended that the Neuro Sense feature be turned ON at the end of the in-clinic testing visit unless the patient prefers the Neuro Sense OFF setting. All subjects will then be followed for up to 24-months following device activation; scheduled study visits will occur at 3-, 6-, 12-, 18-, and 24-months post device activation.

Figure 5-1 is a flow diagram of how subjects will complete the study and Figure 5-2 is a flow diagram of how subjects will go through in-clinic testing.

Figure 5-1 Study Flow Diagram

[figure not shown]
[figure not shown]

Figure 5-2 In-Clinic Testing Flow Diagram

6. Determination of Sample Size

[REDACTED]

[REDACTED]

[REDACTED]

[REDACTED]	[REDACTED]	[REDACTED]	[REDACTED]	[REDACTED]
[REDACTED]	[REDACTED]	[REDACTED]	[REDACTED]	[REDACTED]
[REDACTED]	[REDACTED]	[REDACTED]	[REDACTED]	[REDACTED]
[REDACTED]	[REDACTED]	[REDACTED]	[REDACTED]	[REDACTED]
[REDACTED]	[REDACTED]	[REDACTED]	[REDACTED]	[REDACTED]
[REDACTED]	[REDACTED]	[REDACTED]	[REDACTED]	[REDACTED]

For the primary objective, a subset (28) of the total device implanted low-back and/or leg pain subjects are needed to evaluate the endpoint. For the secondary objectives, up to 45 implanted subjects with low back and leg pain are desired to characterize the responder rates at the 3-Month Visit. Up to 9 implanted subjects with upper limb and neck pain are desired to characterize the population at the 3-Month Visit.

[REDACTED]

[REDACTED]

7. Statistical Methods

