4.2 Purpose

The purpose of the Closed-Loop SCS study is to further our understanding of closed-loop SCS in patients implanted with the Inceptiv INS. The Closed-loop SCS study is a prospective, multi-center, randomized,

[REDACTED]

[REDACTED]

[REDACTED]

6. Study Design

The study is expected to be conducted at up to ten study sites located in Australia. Up to 140 subjects will be enrolled in the study to ensure up to 57 subjects with low-back and/or leg pain and up to 12 subjects with upper limb and/or neck pain are implanted with the study device.

Up to 110 Inceptiv devices may be used in the study. To reduce the possibility of atypical results from a site overly influencing the study, no more than 20% of the total implanted population will be from each site unless the site gets pre-approval from Medtronic for additional implants.

Subjects will be enrolled, and baseline data will be collected. Those meeting all inclusion criteria and no exclusion criteria will undergo a device trial. Subjects with sufficient pain relief during the trial will be implanted with the study device and undergo Device Optimization for 1-Month. Approximately 1-Month post Device Activation, subjects will undergo in-clinic testing. Subjects will be randomized at the in-clinic visit to one of the two sequences: Neuro Sense On followed by Neuro Sense Off or Neuro Sense Off followed by Neuro Sense On. Subjects will be blinded to the settings tested. In each setting, subjects will perform a series of activities and asked to rate the intensity of the overstimulation sensation they experienced while performing the activity using a 5-point Likert scale. [REDACTED]

[REDACTED] It is recommended that the Neuro Sense feature be turned ON at the end of the in-clinic testing visit, unless the patient prefers the Neuro Sense OFF setting. All subjects will then be followed for up to 24-months following device activation; scheduled study visits will occur at 3-, 6-, 12-, 18-, and 24-months post device activation.

[REDACTED]

[REDACTED]

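### Does the smaller study size printed in SAP Section 5, beside two differently based site limits in the protocol, call for a change to the plan?

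*SAP*

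**What the plan says.** SAP Section 5 (Investigation Plan) opens with the size of the study: "Up to 90 subjects will be enrolled in the study to ensure up to 50 subjects with low-back and/or leg pain". For the second pain group its ceiling reads "up to 10 subjects with upper limb and neck pain are implanted with the study device". On hardware it says "Up to 100 Inceptiv devices may be used in the study" and, citing experience from previous studies, "it is estimated that each study site will enroll approximately 9 subjects".

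Protocol Section 6 (Study Design) has larger figures. For enrolment and the main pain group it says "Up to 140 subjects will be enrolled in the study to ensure up to 57 subjects with low-back and/or leg pain". The second pain group has the ceiling "up to 12 subjects with upper limb and/or neck pain are implanted with the study device". The hardware limit there is "Up to 110 Inceptiv devices may be used in the study". Section 10.8 (Baseline) repeats the 140, 57 and 12.

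Protocol version 4.0 is dated 06JAN2023. The SAP history records "Version date on title page corrected from 13-JAN-2023 to 27-JUL-2023", and both of those dates are later than the protocol's.

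On concentration of subjects at one site, protocol Section 14.9 sets a maximum of 18 enrolled subjects per site unless the sponsor agrees beforehand. Protocol Section 6, SAP Section 5 and SAP Section 7.3 set a maximum of 20% of the implanted population, also open to sponsor pre-approval. The waiver refers to extra implants in protocol Section 6 and to extra enrolments in the SAP.

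**The concern.** A SAP dated after a protocol amendment should describe the amended trial. Here all four ceilings in SAP Section 5 differ from the current protocol. The protocol's version history confirms the direction for two of them (90 to 140 enrolled, 50 to 57 low-back/leg implants). A reader could ask which study size the analyses were planned for, and whether the sample-size reasoning was updated too.

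The site limit raises a second question. It is listed as a control on bias, so its base should be clear. The figure 18 is exactly 20% of 90, which suggests a share of the former total that was not updated when enrolment rose. If so, the limit would now sit on two bases, one of them outdated, and sites might not know which applies.

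At stake would be the link between the SAP and the trial actually run, and the strength of the safeguard against one site dominating the result.

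**Working it through.** **Step 1: does the primary sample size depend on the totals?** Inputs from the protocol synopsis: null proportion 0.50, alternative 0.80, one-sided alpha 0.025, n = 28, power above 90%. With an exact binomial test, the smallest success count that keeps alpha within 0.025 is 20 of 28.

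- Alpha: P(X ≥ 20 | n = 28, p = 0.50) = 0.0178
- Power: P(X ≥ 20 | n = 28, p = 0.80) = 0.910

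The stated power is reproduced. Enrolment, implant and device ceilings do not enter the calculation.

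**Step 2: size of the mismatch.**

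| Ceiling | SAP 5 | Protocol | Difference |
|---|---|---|---|
| Enrolled | 90 | 140 | 50 |
| Low-back/leg implanted | 50 | 57 | 7 |
| Upper-limb/neck implanted | 10 | 12 | 2 |
| All implanted | 50 + 10 = 60 | 57 + 12 = 69 | 9 |
| Devices | 100 | 110 | 10 |

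**Step 3: do the numbers used for analysis agree?** The visible text of SAP Section 6 and the sample-size paragraph just before protocol Section 14.9 give the same three targets: 28 for the primary objective, up to 45 low-back/leg subjects at 3 months, and up to 9 upper-limb/neck subjects at 3 months. Each fits under either set of ceilings:

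- 45/50 = 90% and 45/57 = 79%
- 9/10 = 90% and 9/12 = 75%

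The larger protocol ceilings leave more room for attrition around the same targets.

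**Step 4: does any rule use the totals?** SAP Section 7.1.3 defines its sets by what happens to subjects: consented, implanted, the first 28 randomised, or with data at baseline and follow-up. The trigger for multiple imputation is an observed missing fraction above 5%. The pooling rule in SAP Section 7.3 works on observed site counts, with a threshold of 5 subjects. The primary analysis is timed by 28 subjects completing in-clinic testing, and the final analysis by all subjects completing the study. None of these uses 90, 140, 60 or 69.

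**Step 5: site limits.** Taking 20% of each printed total:

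- 0.20 × 90 = 18
- 0.20 × 140 = 28
- 0.20 × 60 = 12
- 0.20 × 69 = 13.8, so 13 whole subjects

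Only the 90 gives 18. On the current total, 18/140 = 12.9%.

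To see which limit is tighter, take the ratio of the protocol's ceilings as an illustrative yield: 69/140 = 49%. Then 18 × 69/140 = 8.9, or about 9 implants, against 13 under the 20% rule. The enrolment limit would be the looser one only if at least 14 of 18 subjects were implanted (14/18 = 78%).

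Reaching 140 with 18 per site needs 140/18 = 7.8, so 8 of the up to ten sites. Ten sites could supply 10 × 18 = 180.

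**Step 6: effect of replacing 18 enrolled by 20% of implanted.** Thirteen implants at a 49% yield correspond to 13/0.493 = 26 enrolled. One site could then go from about 9 implants to 13, and from 18 enrolled to about 26.

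**Step 7: the per-site estimate.** At up to ten sites, 10 × 9 = 90, whereas 140/10 = 14. The SAP attributes the 9 to previous studies. It is an expected count and the 140 is a ceiling, so the gap does not show an error.

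**The case for a change.** The strongest case for a change is that the SAP is the prespecified record and says it rests on the protocol. Disposition and attrition will be reported against planned numbers, and a SAP dated months after the amendment should not carry the old ones. The correction would be text only.

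The case on the site limit also has force. The version 3.0 log gives an expected 20% as one reason for the 18, and only the former 90 reproduces it. The same amendment changed Section 14.1.3 from enrolled to implanted subjects, which might mean that Section 14.9 was left behind. At the site-selection rate of at least one patient a month, a site active throughout the roughly 24 months of enrolment would reach 18 at about month 18, so the limit can bind.

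The first part stands as fact: the SAP figures do not match the current protocol. It does not stand as a reason for action, because actual disposition will be reported and the protocol sets the ceilings.

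The second part stands only as an inference. The current Section 14.9 names no percentage, and the log describes superseded text, so it cannot show that the current text is wrong. The log also cites what sites had been told, and version 3.0 edited Section 14.9 while keeping it on enrolled subjects. That is compatible with two deliberate limits. A limit that binds late in recruitment is doing its job, and the sponsor can waive it.

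**Conclusion.** The concern does not call for a change. The SAP Section 5 totals are a clerical slip in a descriptive paragraph: 50 enrolled, 7 and 2 implanted, and 10 devices below the protocol. The protocol governs recruitment and states 140, 57 and 12 in two places. The analysis targets agree across the documents, the primary test is unaffected (n = 28, alpha 0.0178, power 0.910), and correcting the paragraph would alter neither the conduct of the trial nor any result.

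The two site limits restrict different quantities, can both be met and can both be waived. On the protocol's ceilings the fixed count is the tighter, about 9 implants against 13, so merging them onto the 20% base would weaken the control at the cost of a protocol amendment with ethics and site approvals. Leaving them as they are is a fair trade-off. The per-site estimate and the two waiver wordings have no consequence for the analysis.

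This rests on three assumptions. The 49% yield is a ratio of two ceilings and not an observed rate; the ordering of the limits would reverse only at 78% or more. The redacted parts of the sample-size sections are assumed to contain no rule that uses these totals. The SAP title page and the text of protocol Section 14.1.3 are not available, so neither the protocol version that the SAP names nor the full site rule can be checked. The log gives no former value for the 10 or the 100, so those two differences rest on comparing current texts alone.

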7.1 Study Subjects

7.1.1 Disposition of Subjects

Subject disposition will be illustrated in a flow diagram. Subject visits will be tabulated and compliance to visit schedule will be summarized. Attrition will be identified and summarized.

7.1.2 Clinical Investigation Plan (CIP) Deviations

All CIP deviations will be summarized by the type of deviation. Details of CIP deviations that affect scientific integrity and subject safety may be presented.

7.1.3 Analysis Sets

- The **All Consented Set** (ACS) will include all subjects who signed the study specific ICF and enrolled in the study.
- The **Full Analysis Set** (FAS) will include all device-implanted subjects.
- The **Primary Analysis Set** (PAS) will follow the intent-to-treat (ITT) principle to include randomized low-back and leg pain subjects who will be used for the primary objective, i.e., the first 28 randomized low-back and leg pain subjects.
- The **Complete Case Set** (CCS) will include all device-implanted subjects who have data available at baseline and follow-up. This set is defined for each outcome measure at each follow-up visit. [REDACTED]

[REDACTED]

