14.4 Primary Objective

The primary objective is to demonstrate that the proportion of low-back and/or leg pain subjects having a reduction in overstimulation sensation with Neuro Sense On compared to Neuro Sense Off, at the randomization and in-clinic testing visit, exceeds a performance goal of 50%.

Overstimulation is defined as an uncomfortable sensation of stimulation (intense tingling, shocking, jolting) brought about by protocol-prescribed activities [REDACTED]. This overstimulation sensation is transient and reversed by the subject returning to a neutral position.

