7.6 Demographic and Other Baseline Characteristics

Demographic and other baseline characteristics will be summarized for the ACS, PAS, and FAS datasets. Summaries of age at baseline, sex, race, ethnicity, primary indication, primary location of pain (low back/leg, upper limb-not neck, upper-limb neck), and medical history will be included. Additionally, we will summarize the baseline outcome measures for the ACS, PAS, and FAS datasets by primary location of pain.

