7.9.1.1 Hypothesis

It is hypothesized that the proportion of low-back and leg pain subjects with a reduction in overstimulation sensation during Neuro Sense On compared to Neuro Sense Off period exceeds a performance goal of 50%.

$$H_0: p \leq 50\%$$

$$H_A: p > 50\%$$

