7.9.1.5 Analysis Methods

The proportion of low-back and/or leg pain subjects with a reduction in overstimulation sensation during Neuro Sense On compared to Neuro Sense Off period will be calculated, with a one-sided 97.5% confidence lower bound. This proportion will be tested against 50% using a binomial exact test. The confidence lower bound needs to be greater than 50%, or equivalently, the p-value must be less than 0.025 to reject the null hypothesis.

[Redacted text block]

[Redacted text block]

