7.9.1.6 Determination of Subjects/Data for Analysis

The primary analysis for the primary objective will follow the ITT principle by including the low-back and/or leg pain subjects randomized for the primary analysis (PAS). If more than 5% of the average intensity scores for either the OL or CL period are missing, then the subjects who are randomized but have missing average scoring of overstimulation sensation during Neuro Sense On and/or Neuro Sense Off period will be imputed using Multiple Imputation (MI) as described in 7.4.

[Redacted text block]

[Redacted text block]

[Redacted text block]

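### Does the SAP's 'low-back and leg pain' wording leave single-site subjects out of the primary analysis set?

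*SAP*

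**What the plan says.** The SAP describes the primary population in two ways.

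With *and*: the primary objective in SAP 4.1, repeated in 7.9.1, concerns "the proportion of low-back and leg pain subjects having a reduction in overstimulation sensation". The hypothesis in 7.9.1.1 reads "It is hypothesized that the proportion of low-back and leg pain subjects with a reduction in overstimulation sensation". The set definition in 7.1.3 ends with "the first 28 randomized low-back and leg pain subjects".

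With *and/or*: the sample-size text in SAP 6 says "a subset (28) of the total device implanted low-back and/or leg pain subjects are needed to evaluate the endpoint". SAP 7.9.1.5 computes and tests the "proportion of low-back and/or leg pain subjects with a reduction in overstimulation sensation". SAP 7.9.1.6 builds the analysis by "including the low-back and/or leg pain subjects randomized for the primary analysis (PAS". SAP 7.9.1.4 also has *and/or*.

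The protocol's primary objective (14.4) concerns "the proportion of low-back and/or leg pain subjects having a reduction in overstimulation sensation", and Protocol 14.4.1.1, 14.4.1.5 and 14.4.1.6 agree. Inclusion criterion 3 (Protocol 9.3) requires overall VAS of at least 60 mm and accepts a qualifying score at the back, the leg or both.

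Separately, SAP 5 gives up to 90 enrolled, 50 low-back/leg and 10 upper-limb/neck implants, and 100 devices. Protocol 6 gives 140, 57, 12 and 110.

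**The concern.** A formal analysis-set definition normally governs. If *and* in SAP 7.1.3 means that each subject must have both pains, the definition excludes people whom criterion 3 deliberately admits. The 28 subjects in the only hypothesis test would then differ from the 28 described by the protocol and by the SAP's analysis rules. The set would fill more slowly, and the result would apply to a narrower population.

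The outdated counts in SAP 5 add to the impression that the SAP was not brought into line with the current protocol. Its title-page date was corrected to 27-JUL-2023, more than six months after Protocol v4.0 of 06JAN2023.

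**Working it through.** **1. Reproduce the planned 28.** Inputs: null proportion 0.50 and alternative 0.80 (Protocol synopsis, Statistics); exact binomial test at one-sided 0.025 (SAP 7.9.1.5).

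Type I error for the rule *reject at r or more*: Σ C(28,k)/2^28 for k = r to 28.
- r = 19: 0.0436, too large.
- r = 20: 0.0178, below 0.025. The cut-off is 20.

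Power at 0.80: Σ C(28,k)·0.8^k·0.2^(28−k) for k = 20 to 28 = 0.910.

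Smaller sizes fall short: n = 27 (cut-off 20) gives 0.844 and n = 25 (cut-off 18) gives 0.891. The stated figure of 28 for more than 90% power is therefore right. No input depends on pain location, so the wording bears only on who the 28 are.

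**2. Set the texts side by side.**

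| Place | Function | Wording |
|---|---|---|
| SAP 4.1, 7.9.1 | objective | and |
| SAP 7.1.3 | set definition | and |
| SAP 7.9.1.1 | hypothesis | and |
| SAP 6, 28-subject sentence | sample size | and/or |
| SAP 7.9.1.4 | rationale for the goal | and/or |
| SAP 7.9.1.5 | estimate and test | and/or |
| SAP 7.9.1.6 | data selection, names the set | and/or |
| Protocol 14.4 and subsections | objective, hypothesis, test, set | and/or |

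The SAP sections that tell the analyst what to compute and on whom all say *and/or*, and so does the parent protocol.

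**3. Test whether *and* can mean both pains.** SAP 5 and 6 call the second cohort upper limb *and* neck pain, where the protocol has *and/or*. Yet SAP 7.6 classifies subjects by "primary location of pain (low back/leg, upper limb-not neck, upper-limb neck", which includes a group with upper limb pain and no neck pain. In that label *and* cannot require both sites. It joins the members of one cohort, and *low-back and leg pain subjects* reads naturally in the same way. SAP 7.6 also treats low back/leg as a single category. No visible text names a both-pains subset or gives a threshold for one.

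**4. Check the SAP 5 counts.**
- Enrolled: 140/90 − 1 = 55.6% higher in the protocol.
- Implanted: (57 + 12)/(50 + 10) − 1 = 69/60 − 1 = 15.0% higher.
- Devices: 110/100 − 1 = 10% higher.

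The protocol's version history confirms 90 to 140 and 50 to 57. It does not state earlier values for the 12 or the 110, so calling 10 and 100 outdated is an inference. The figures that serve the objectives agree across the two documents: 28 for the primary objective, up to 45 for the secondary objectives, and up to 9 upper-limb/neck subjects. The site limit in SAP 5 and 7.3 is a percentage of implanted subjects, so it does not use the old counts either.

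**The case for a change.** The best case for amending is that a set definition should not need interpretation from other sections. The Primary Analysis Set serves the only hypothesis test. It is also used for baseline summaries (SAP 7.6) and, according to the SAP version history, for some additional objectives at 3 months. Single-site subjects are expected: Protocol 14.5.2 analyses back and leg responders in separate subsets. The repair would cost a few words.

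What stands is that the wording is uneven and the SAP 5 counts are out of date. What does not stand is a demonstrated effect on the analysis.

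Sizing the harm requires a definition that the documents lack. One could require 60 mm at both sites, but a subject with leg VAS 80 and back VAS 40 also has both pains, and nothing visible settles which would count. Nor is the pool for such a calculation the 57 implanted subjects, because Protocol 10.15 and 10.15.2 randomize only those with a clear, measurable ECAP. The advice in Protocol 10.8 that at least 25 of the 57 have back VAS of 60 mm or more is a recommendation about back pain. It neither bounds nor estimates the number with both pains. Any shortfall computed on these lines would describe a reading that the rest of the plan rejects.

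Two limits remain. The protocol's own analysis-set section is not in the available text, so the two formal definitions cannot be compared directly. The SAP title page is also absent, so the protocol version it cites cannot be seen.

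**Conclusion.** No change to the plan is called for. The variation between *and* and *and/or* is a clerical slip, and an analyst would resolve it correctly from SAP 7.9.1.6, the 28-subject sentence in SAP 6 and Protocol 14.4. Under that reading n stays at 28, the cut-off at 20, the attained one-sided level at 0.0178 and power at 0.910. The SAP 5 counts are descriptive ceilings that feed no analysis.

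This conclusion assumes that the 28 were chosen under *and/or*. The weight of the text supports that, but the documents cannot prove what was done. It does not address the separate question of whether the 28 are the first randomized (SAP 7.1.3) or the first to complete testing with an endpoint (SAP 7.4).
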